8. SUMMARY OF STUDY DATA

All continuous variables will be summarized using the following descriptive statistics: n (non-missing sample size), mean, standard deviation, median, maximum and minimum (as applicable). The frequency and percentages (based on the non-missing sample size) of observed levels will be reported for all categorical measures. In general, all data will be listed, sorted by study arm and subject, and when appropriate by outcome within subject. All summary tables will be structured with a column for each intervention and will be annotated with the total population size relevant to that table, including any missing observations.

a. Subject Disposition

We will identify participants to be included in ITT based on randomization assignment among all those contacted. Allocation assignment will be assessed using categorical variable assigned (defined as Arm 1- Arm 12) assigned at the time of randomization and stored within the survey platform. In order to identify patients who have completed the survey (primary outcome) or partially completed the survey (secondary outcome), we will use variables assessed from the survey platform (WaytoHealth) for each subject. The survey questions are coded based on the response (Yes =1; No=0) for each of the three questions. We will also conduct visual evaluation (i.e., review text responses) for any question where the natural language processing is less than 90% confident (as assigned by the survey platform). Below is a draft consort diagram that to be populated with number and proportion of participants in each cell.

b. Derived variables

The survey platform (WaytoHealth) uses natural language processing to interpret the text-based response
SAP version V.1 (November 25, 2023)

into a derived variable (Yes or No), using a pre-specified confidence threshold of 0.9. For any response, that does not reach this confidence threshold, the platform asks for clarification (i.e., “Please answer Yes or No”) from the participant. To ensure quality of the derived variables, we will review a random sample of questions that classified as yes or no (50 each). If we identify that more than 5% are misclassified by the platform, then we will review all responses. For any survey responses with a confidence threshold lower than 0.9, two members of the analytic team will independently review each response for interpretation and classification. If no agreement is reached, the survey response will be marked as unknown.

c. Protocol Deviations

We do not anticipate any major protocol deviations that could impact analysis, but one that would require adjustments would be if participants receive a different intervention than they are assigned to receive. This unlikely event might happen if there is an error in the programming code within WaytoHealth. Prior to analysis, we will review a subset of 50 randomly selected participants to review the content of all intervention messages received and assess concordance with their assigned study arm. If we identify that more than 5% received an incorrect intervention message, we will review all participants to ensure we have correctly classified them in the right intervention arm. After this, we will conduct subgroup analysis with and without misclassified participants to understand the impact on analysis and report our findings. Any misclassified participants might be excluded primary analysis depending upon subgroup analysis and reported as such.

d. Demographic and Baseline Variables

| Demographics and Baseline Variables | Source |
|---|--------|
| Age at index date | EHR |
| Race | EHR |
| Ethnicity | EHR |
| Sex | EHR |
| Sexual Orientation and Gender Identity | EHR |
| Socioeconomic Status (Based on Census-Tract) | EHR |
| Tobacco Use (Current, Former, Never, Unknown) | EHR |
| Pack-Years (Lifetime Smoking) | EHR |
| Other Smoking Data (E.g., Quit Date, Types) | EHR |

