5. STUDY METHODS

a. General Study Design and Plan

This single-blind study uses a 3x2x2 factorial design. Upon confirmation of their name, patients are randomized to one of the 12 potential study arms immediately based on two stratification variables (race and sex). If the patient does not confirm their name via text message, the patients will not be randomized nor included in the study. Upon randomization, the participants immediately receive the assigned interventions via text message.

| 3x2x2 Study Design | Tobacco Use Message A | | Tobacco Use Message B | |
|------------------------|-----------------------|--------------|-----------------------|--------------|
| | Incentive | No Incentive | Incentive | No Incentive |
| Introductory Message A | Arm 1 | Arm 2 | Arm 3 | Arm 4 |
| Introductory Message B | Arm 5 | Arm 6 | Arm 7 | Arm 8 |
| Introductory Message C | Arm 9 | Arm 10 | Arm 11 | Arm 12 |

b. Inclusion-Exclusion Criteria and General Study Population

Inclusion Criteria: Based on available EMR data at the time of enrollment, patients will be eligible if they:

- meet age eligibility (50-80 years old) for LCS based on 2021 USPSTF guidelines
- have completed at least one primary care visit at Penn Medicine in 2020-2025
- have a mobile phone listed in their medical record
- confirm identify at the time of initial outreach via text message.

Exclusion Criteria: Based on available EHR data at the time of enrollment, patients will be ineligible if they:

- have a documented history of lung cancer
- have a documented history of completing LCS at Penn Medicine
- are listed as not wanting to be contacted or solicited for research
- do not otherwise meet inclusion criteria.

c. Randomization and Blinding

Participants will be randomized into one of 12 study arms at the time of name confirmation. Randomization will occur using the randomization module within the Way-to-Health platform and be stratified by sex (female vs non-female) and race (Black adult vs non-Black adult). Single blinding (statistician) will be used in this study. Participants are randomized in blocks of 24 (12 study arms).

d. Study Assessments

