6. SAMPLE SIZE

To determine the sample size for the trial, we considered a range of hypothesized response rates from 3% to 12% for the 12 arms representing different combinations of messaging and incentives and based on prior research studies. We hypothesized this range of response rates would be plausible for many of the arms and chose the final sample size based on our ability to distinguish statistically two arms towards the extremes of the range. Figure 1 below shows a plot of the 95% confidence intervals for the range of hypothesized response rates (plotted on both x- and left y-axes). With N=6,000 participants total (500 per arm), we would be able to detect a 5-percentage point difference between two arms if one of the arms had a response rate of 3% to approximately 7%. In comparison, with N=3,600 we would only be able to detect a 5-percentage point difference between two arms if one of the arms had a response rate of 3% or lower. Although larger samples would allow us to detect smaller differences, piloting on a larger sample would decrease the number of participants available for future trials. Balancing this logistical concern with power to detect differences between arms, we chose to include N=6,000 participants in this pilot study.

[figure not shown]

Figure 1: Illustration of 95% confidence interval length for potential response rates between 3% and 12%. Response rates are plotted on both the x- and y-axes. Each panel plots confidence intervals for the total sample size (N) given on the right y-axis.

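### The message-delivery check requires no action after one or two confirmed wrong messages, so a fault confined to one arm could go without full review

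*SAP*

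**What the plan says.** SAP section 8c (Protocol Deviations) singles out one deviation that would call for adjustment: "if participants receive a different intervention than they are assigned to receive". On how it could arise, it says "This unlikely event might happen if there is an error in the programming code within WaytoHealth".

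The safeguard is a single check before analysis: "we will review a subset of 50 randomly selected participants to review the content of all intervention messages received", to be compared with the assigned arm. The action rule is "If we identify that more than 5% received an incorrect intervention message, we will review all participants". Analyses with and without misclassified participants come after that full review.

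The section does not say that the 50 are spread over the arms. It gives no action for discordant records at or below 5%, and no probability that the check would miss a fault.

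On the design, SAP section 5c states "Participants are randomized in blocks of 24 (12 study arms") and SAP section 6 states "With N=6,000 participants total (500 per arm").

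**The concern.** The rule treats wrong messages as if they were scattered clerical errors, of which a few per cent can be tolerated. The cause that the SAP names is different in kind. A fault in messaging code repeats for everyone who follows the faulty branch, so one confirmed wrong message is evidence of a problem that may affect many others. The written rule nevertheless lets two such findings pass without further work.

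One arm is a twelfth of the trial, which is not far above the 5% trigger. A fault confined to one arm is therefore the kind that a random 50 with this trigger handles least well.

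The primary analysis in SAP section 9a uses participants as randomized. If a fault in one arm were not followed up, that arm's responses would be credited to a message it did not send. This would bias the response rate of that message combination, and it would affect the first-stage incentive test if the incentive wording were wrong. The with-and-without analyses would not help, because they follow only from a full review.

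**Working it through.** **Inputs from the SAP**
- Check size: 50, a simple random sample as the text reads (section 8c).
- Trigger: more than 5% of 50 = more than 2.5, so 3 or more discordant records (section 8c).
- 12 arms and 6,000 participants (sections 5c and 6).

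**The plan's own figure.** 6,000 / 12 = 500 per arm, as stated in section 6. One arm is 500 / 6,000 = 1/12 = 8.3% of participants. The SAP gives no miss probability to reproduce.

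**Assumption.** The extent of a fault is not in the SAP, so several extents are shown. For a fault affecting a share p of participants, the number X of discordant records among 50 is taken as Binomial(50, p). Full review is not triggered if X is 2 or less.

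**One arm wholly wrong, p = 1/12.** Expected discordant records: 50/12 = 4.17.
- P(0) = (11/12)^50 = 1.3%
- P(1) = 50 × (1/12) × (11/12)^49 = 5.9%
- P(2) = 1,225 × (1/12)^2 × (11/12)^48 = 13.1%
- P(X ≤ 2) = 20.2%. The exact hypergeometric value (500 of 6,000, sample of 50) is 20.1%.

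About 19 of the 20 points (5.9 + 13.1) are therefore cases in which at least one wrong message is seen but the rule requires nothing more.

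**Other extents, and a changed trigger with the same 50 records**

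| Extent of fault | Share p | Not triggered, SAP rule (X ≤ 2) | Not triggered if any error counts (X = 0) |
|---|---|---|---|
| Half of one arm | 1/24 | 65.4% | 11.9% |
| One arm | 1/12 | 20.2% | 1.3% |
| Two arms | 1/6 | 0.7% | 0.01% |
| One introductory-message level (four arms) | 1/3 | below 0.0001% | below 0.0001% |

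**Sampling five per arm (60 records) with any error as trigger.** A wholly wrong arm yields five discordant records out of five, so the miss is 0%. If half of one arm is wrong, the miss is 0.5^5 = 3.1%.

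**A larger sample under the present rule.** For one wholly wrong arm, a simple random sample with the 5% trigger misses 15.1% at 100 records and 5.0% at 200. Changing the trigger does more than adding records.

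**Effect on the choice of message.** Section 9a compares six message combinations. A sole winner needs a lower confidence limit above the upper limits of all the others. Suppose one arm is sent the message of another compared arm, with 500 in each. Both then have the same true rate and nearly the same standard error, s. The mislabelled arm clears its twin only if the observed difference exceeds 2 × 1.96 × s, while that difference has standard error √2 × s. So z = 2 × 1.96 / √2 = 2.77, with an upper-tail probability of about 0.3%.

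**The case against.** The strongest reply has four parts.

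- **The scenario is assumed.** The SAP describes only the general event and calls it unlikely. No document gives the probability of a fault or says that it would strike exactly one arm. In a 3x2x2 design a coding error could as easily affect a whole factor level or swap two arms, and the existing check would almost always catch either. This stands. The 20% is conditional on a fault in one arm.
- **The check would rarely see nothing.** A reader might infer from the 20% that the check is blind to a wholly wrong arm one time in five. The documents do not support that, since no discordant record appears only 1.3% of the time. The SAP sets when full review is mandatory and does not forbid acting on less, so a careful team might well act on one or two errors. This also stands, but a pre-specified rule should not depend on the team exceeding it.
- **The harm is narrower than it may appear.** A reader might infer that a mislabelled arm could readily become the adopted message. Under section 9a that is improbable when the arm shares its true rate with another compared arm (about 0.3%). A swap could create a false sole winner, but that is the two-arm case, missed 0.7% of the time. If the incentive effect is not significant, each combination pools two arms, and one bad arm is only half of it. What remains is mainly a masked winner or a blurred set of leading combinations. There is also some effect on the incentive test, where one arm is 500 of the 3,000 on its side.
- **The setting is modest.** The protocol (Methods, section 3) treats the message comparison as exploratory and secondary, and SAP section 6 describes a pilot. This lowers the severity but does not make the trigger suitable for the fault it is meant to find.

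**Conclusion.** The point holds as a minor weakness in a stated rule. The trigger in SAP section 8c does not fit the cause that the SAP itself names, because it requires no follow-up after one or two confirmed wrong messages. If exactly one of 12 arms were wholly wrong, full review would not be triggered about 20% of the time; if half of one arm were wrong, about 65%. Faults in two arms or in a whole introductory-message level would be caught.

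These figures assume a simple random 50, equal allocation and a fault confined to one arm. The protocol (Methods, section 3) allows assignment to be adapted, and an arm with a smaller share would be missed more often. They are not the probability that the trial contains an undetected error, which the documents give no means to estimate. Nor do they show that a wrong message would be adopted.

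**What to change.** **Main change.** Reword SAP section 8c so that any discordant message in the checked sample leads to review of all participants. With the same 50 records, the probability of missing a single-arm fault falls from 20% to 1.3% for a full arm and from 65% to 12% for half an arm. Most of the gain comes from this step.

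**Refinements**
- Draw five participants from each arm (60 records), keeping the any-error trigger. The miss becomes 0% for a full arm and about 3% for half an arm.
- Alternatively, if the platform can export its outgoing-message log, compare it by script with the assigned arm for everyone randomized. This removes sampling error.
- Run the check early in enrolment as well as before analysis, so that a fault can be found while it can still be corrected.

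**Cost.** A change of SAP wording, and ten more records to read or a short script. The downside is an occasional full review prompted by what proves to be an isolated error.

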7. GENERAL ANALYSIS CONSIDERATIONS

a. Timing of Analyses

The final analysis will be performed when at least 6,000 participants have randomized. The final analysis will be performed after all necessary cleaning and approval of statistician and after the finalization and approval of this SAP document.

b. Analysis Populations

i. Intention to Treat

All subjects who were randomized will be included in the intention to treat analysis. This will be the primary efficacy population for the purposes of the study.

ii. Per Protocol Population

All subjects who responded in any form (e.g., any text message response including but not limited to survey response) after receiving the intervention (i.e., after all interventions are delivered) will be included in the per protocol analysis. This will be the secondary efficacy population for the purposes of the study. This will exclude participants in the ITT that only confirmed their name and did not reply in any form after that.

c. Covariates and Subgroups

Covariates including baseline demographic (e.g., age, race, sex, ethnicity) and smoking history data (e.g., tobacco use status, lifetime smoking) will be extracted from the EHR. Variables used in randomization (sex and race) will be adjusted for in the primary analysis. We will assess baseline characteristics of each group by key covariates to assess any potential differences. Given persistent disparities in lung cancer by race and in LCS guidelines by race and sex, we will conduct exploratory subgroup analysis to assess potential treatment heterogeneity by race (Black adults vs Non-Black adults) and sex (female vs non-female). We do not hypothesize that our treatment will be different for each group, but given disparities, we conduct exploratory analysis to assess heterogeneity of treatment effects by race and sex.

d. Missing Data

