9. EFFICACY ANALYSES

a. Primary Efficacy Analysis

All summary statistics will be produced in accordance with section 8, and all primary efficacy analyses will use the ITT population. All tests will be two-sided and use a Type I error of 0.05. First, we will test for a main effect of incentive versus no incentive using an independent proportions Z-test. If this main effect is significant, we will proceed to study the two messaging factors using only data from individuals randomized to the incentive condition with higher response rate. If the main effect of incentive is not significant, we will proceed with studying the two messaging factors using all data and assuming incentive level does not interact with messaging or have any other effect on the outcome. Next, using either half or all the data, we will model the binary indicator of complete survey response or non-complete survey response within 7 days using a logistic regression. The model will adjust for race and sex and will incorporate 5 indicators of treatment arm (3 introductory messaging levels x 2 tobacco use messaging levels – 1 reference group). We will compute the marginal response probability for each arm, averaging over the observed distribution of sex and race. Standard errors and 95% confidence intervals will be obtained for each marginal response probability using the delta method. If one of the confidence intervals has a lower limit that exceeds the upper limit of all the others, its corresponding set of factor levels will be used in the primary study, pending confirmation that exploratory analyses do not raise red flags about disparities in response rates. If a set of confidence intervals have lower limits that surpass the upper limits of the other intervals, the final choice of factor levels to use will be based on discussions amongst the study team and key stakeholder, taking into consideration the point estimate, confidence interval length, and exploratory data on disparities.

i. Secondary Analyses of Primary Efficacy Endpoint

We will conduct secondary analyses of the primary efficacy endpoint using the per protocol, instead of the ITT population, to assess if documented engagement after receipt of the full intervention affected efficacy.

ii. Analyses of Secondary Endpoints

We will conduct similar analysis outlined in Section 9a to assess the effect of the interventions on the secondary outcome, partial completion of the survey.

b. Exploratory Efficacy Analyses

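### SAP 8.c lets a comparison of results decide, with no criterion, whether misdelivered participants leave the primary analysis; separately, the per protocol set keeps only repliers and is not a randomized comparison

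*SAP*

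**What the plan says.** **Primary population.** SAP 7.b.i states "All subjects who were randomized will be included in the intention to treat analysis" and makes this the primary efficacy population. SAP 8.a adds "We will identify participants to be included in ITT based on randomization assignment among all those contacted", and SAP 9.a says that "all primary efficacy analyses will use the ITT population".

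**Misdelivery.** SAP 8.c (Protocol Deviations) considers participants receiving a message other than the one assigned: "This unlikely event might happen if there is an error in the programming code within WaytoHealth". Fifty randomly chosen participants are audited. If more than 5% are wrong, everyone is reviewed. Then "we will conduct subgroup analysis with and without misclassified participants to understand the impact on analysis and report our findings", followed by "Any misclassified participants might be excluded primary analysis depending upon subgroup analysis and reported as such". The 5% figure triggers the full review; it does not govern exclusion.

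**Incentive gate.** SAP 9.a tests incentive against no incentive first. "If this main effect is significant, we will proceed to study the two messaging factors using only data from individuals randomized" to the better-responding incentive condition; otherwise all the data are used.

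**Per protocol.** SAP 7.b.ii includes "All subjects who responded in any form (e.g., any text message response including but not limited to survey response) after receiving the intervention" and drops those who only confirmed their name. It is called the secondary efficacy population, and 9.a.i repeats the primary-endpoint analysis in it.

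**The concern.** **Exclusion under 8.c.** Whether misdelivered people stay in the primary analysis is settled after both sets of results are seen, with nothing saying what size or direction of difference would lead to exclusion. An analysis that removes randomized participants is no longer the intention-to-treat analysis that 7.b.i and 9.a promise. The choice also feeds the incentive gate, and so decides whether the messages are studied in half or all of the 6,000.

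**Per protocol under 7.b.ii.** Randomization happens at name confirmation, before the messages are sent. A later reply is therefore a post-randomization event, one that the messages and incentive are intended to influence, and nobody can meet either endpoint in 4.b without replying. The set says nothing about whether the assigned message was delivered. It keeps every completer and removes only silent non-completers. An arm that draws more replies gets a larger denominator, so its completion rate among repliers can fall although it produced more completed surveys.

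**Working it through.** **Inputs from the SAP.** 6,000 randomized in 12 arms of 500, so 3,000 per incentive level in six message cells; response 3–12% (section 6); two-sided 0.05 (9.a); audit of 50, with more than 5% meaning 3 or more (8.c). **Assumed:** misdelivery shares and any-reply rates.

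**Check of the SAP's own figure.** Section 6 says that with 500 per arm a 5-point difference is detectable for a lower arm of 3% to about 7%. Solving 1.96·[√(p(1−p)/n) + √(q(1−q)/n)] = 0.05 with q = p + 0.05 gives p = 6.67% at n = 500 and 3.00% at n = 300. Both match the SAP and confirm the inputs.

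Test used below: z = (p₁ − p₂)/√[p̄(1−p̄)(1/n₁ + 1/n₂)], rejecting at |z| > 1.96. Simulated figures use 500,000 trials per scenario.

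**1. Random misdelivery, no true incentive effect (base rates 3, 7.5 and 12%).**

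| Share misdelivered | Keep all | Exclude | Disagree on significance | Smaller p always taken |
|---|---|---|---|---|
| 5% | 0.05 | 0.05 | 2.1% | 0.060 |
| 10% | 0.05 | 0.05 | 2.9% | 0.065 |
| 20% | 0.05 | 0.05 | 4.2% | 0.071 |

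The last column is a worst case that the SAP does not state.

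**2. One whole incentive arm sent the wrong message.** Message cells are set at 5, 6, 7, 8, 9 and 10% on both sides, with no true incentive effect.

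- *Exclude that arm.* Dropping the 5% cell moves the incentive mean from 7.5% to (6+7+8+9+10)/5 = 8.0%, a bias of 0.5 points. SE = √[0.075·0.925·(1/2500 + 1/3000)] = 0.713 points, a shift of 0.70. Rejection ≈ Φ(−1.26) + Φ(−2.66) = 0.11. Simulation: 0.11 (5% or 10% cell), 0.07 (6% or 9%), 0.05 (7% or 8%).
- *Keep everyone.* If the wrong message moves that cell by d points, the bias is d/6. For d = 5 this is 0.83 points. SE = √[0.075·0.925·2/3000] = 0.680 points, so the shift is about 1.22 and rejection about 0.23. Simulation: 0.05 (d = 0), 0.06 (d = 1), 0.11–0.12 (d = 3), 0.22–0.24 (d = 5).

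Neither choice is uniformly better. The defect is choosing after seeing both.

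**3. Replier-only set.** Since every completer has replied, completion among repliers = intention-to-treat completion ÷ reply share. Take true completion of 7% v 9% (intention-to-treat power 82%) and 10% replying in the first group:

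| Reply, second group | Completion among repliers | Significant, right direction | Significant, wrong direction |
|---|---|---|---|
| 10% | 70% v 90% | >99.9% | 0 |
| 12% | 70% v 75% | 30% | <0.1% |
| 12.9% | 70% v 70% | 2.5% | 2.5% |
| 14% | 70% v 64% | <0.1% | 36% |
| 15% | 70% v 60% | <0.1% | 80% |

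Check of the last row: 210/300 v 270/450, pooled 480/750 = 0.64, SE = √[0.64·0.36·(1/300 + 1/450)] = 0.0358, z = 0.10/0.0358 = 2.80, and Φ(2.80 − 1.96) = 0.80.

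With equal completion (7% in both) and replies of 8% v 8.5, 9 or 10%, the replier-only test is significant in 36, 83 and 99.9% of trials. With equal replies of 12% and 60% v 80% of repliers completing, its power exceeds 99.9% against 92% for intention to treat, with no wrong-direction results.

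**4. Audit.** For an error in one arm (1/12 of participants), P(2 or fewer of 50) = 0.20, so the full review would not be triggered about one time in five.

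**The case against.** **On 8.c**, the case against is that the SAP calls the event unlikely, commits to reporting both analyses, has a blinded statistician, and says in 7.e that Type II errors matter more than Type I. The with/without comparison also follows only if the audit triggers. At 5% misdelivery, P(3 or more of 50) = 0.459, so the worst case falls from 0.060 to about 0.05 + 0.459 × 0.010 = 0.055; at 10% it falls from 0.065 to about 0.063. Dropping the matching message cell on the other side as well restores 0.05 in the whole-arm example. Keeping everyone can itself do worse, at 0.22–0.24. All of this is correct, and it limits the size. It does not say which result operates the gate. Blinding to arm labels does not hide whether the two results differ, and a preference for power does not justify a result-dependent population.

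The full review in 8.c is also meant to place people in the right arm. This could mean regrouping by message received, in which case the keep-all figures would not describe the SAP's own analysis with them included. That ambiguity is a further reason to settle the wording.

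**On per protocol**, the SAP openly says who is dropped and that the aim concerns engagement. The reversals need replies to rise 40–50% in relative terms while completion among repliers falls, and nothing in the documents predicts that. This is fair: the scenarios show what could happen, not what is expected. The false differences at equal completion need a much smaller gap, however (8% v 8.5%). The main decision uses intention to treat. One route remains: 9.b repeats the 9.a analyses by race and sex, and 9.a makes the choice subject to exploratory findings on disparities, so on one reading replier-only subgroup results could be consulted.

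**Conclusion.** Both parts hold and should be fixed.

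**8.c** makes the primary population depend on results, with no criterion, against 7.b.i and 9.a. It matters only if misdelivery is detected. The type I inflation is modest if misdelivery is random (at most about 0.07 for shares up to 20%, before allowing for the audit trigger). It can be larger under the programming error that the SAP itself names, whichever option is taken.

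**7.b.ii and 9.a.i** give a non-randomized comparison the label of secondary efficacy. It can hide, reverse or create a difference when arms reply at different rates, and is not distorted in this way when they reply equally. It does not alter the primary intention-to-treat test.

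The textual contradiction and the way the set conditions on replying do not depend on assumed figures. The percentages do: they rest on assumed misdelivery and reply rates, with completion kept within the SAP's 3–12%.

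**What to change.** **8.c.** Analyse everyone in the assigned arm for the primary analysis and the incentive gate. Make exclusion and as-delivered grouping sensitivity analyses that are fixed in advance and always reported. For a whole-arm programming error, state from delivery logs alone, before outcomes are compared by arm, how these analyses will inform the choice of factor levels.

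**7.b.ii and 9.a.i.** Either call the replier-only analysis descriptive (completion among repliers beside each arm's reply rate, with no efficacy inference), or define per protocol by logged delivery of all assigned messages and keep non-repliers in the denominator.

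**Optional.** Compare logged with assigned messages for all participants by program, in place of the 50-person sample.

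**Cost.** SAP wording, plus the log check if adopted. Keeping everyone has two downsides, which the sensitivity analyses would show:

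- *Dilution.* For 7% v 9%, randomly swapping incentive level in 5% of participants shrinks the difference to 1.8 points and power from 82% to 73%; swapping 10% gives 1.6 points and 63%. Excluding those people would give 79% and 77%.
- *Whole-arm error.* A false incentive difference of up to 0.83 points in the 5–10% example, and an estimate for that cell that reflects the wrong message.
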